- Perform adverse event inquiry.
- Perform concomitant medication inquiry.

The start of run-in period visit (visit 2) will take place 3 weeks before the baseline/DoR visit. The following procedures will be performed at visit 2:

- Review inclusion/exclusion criteria.
- Perform vital signs measurements (includes systolic and diastolic blood pressure, pulse, body temperature, and respiratory rate).
- Provide PEF meter to patient.
- Provide asthma control diary to patient.
- Assess asthma exacerbations and related health care utilizations.
- Perform concomitant medication inquiry.
- Perform adverse event inquiry

For a minimum of 3 weeks after visit 2, patients will continue on their usual asthma medications and complete daily self-monitoring of symptoms using an asthma control diary and PEF meter. Level of asthma control will be established based on the frequency of symptoms, use of a SABA, nighttime awakenings due to asthma, and ambulatory lung function.

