**6.10. Asthma Rescue Medication Use**

The number of times asthma rescue medication (number of inhalations/puffs) is used will be assessed by reviewing the asthma control diary. Note: SABA therapy used for exercise pretreatment should not be recorded.

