**6.11. Nighttime Awakenings**

Patients will record nighttime awakenings due to asthma as indicated in the asthma control diary.

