#### **9.5.6.2. Secondary Efficacy Analysis**

All efficacy variables will be summarized by treatment group. For continuous variables, the summary statistics will include n, mean, SD, standard error (SE), median, minimum, and maximum.

Analysis of pulmonary function tests, AQLQ +12, ACQ-6, total asthma symptom scores, and SGRQ use will use the mixed model repeated measures model with treatment group, visit, treatment and visit interaction, baseline value, and stratification factors as fixed effects and patient as a random effect.

Analysis of percentage of asthma control days will use an analysis of variance (ANOVA) model with treatment group and stratification factors.

The Kaplan-Meier (KM) method will be used to estimate and compare the distributions of time to first CAE between treatment groups. Differences will be compared using a log rank test adjusting for the stratification factors.

The frequency of exacerbations requiring hospitalization or emergency department visits and the frequency of moderate exacerbations will be examined separately. The analysis will use similar methodology to that described for the primary analysis.

Additional covariates or factors may be added to the statistical models. These will be detailed in the statistical analysis plan.

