6.3.3.2. Analysis

Summary statistics of actual values and change from baseline to each scheduled visit will be provided by treatment group.

Analysis of the change from baseline to each scheduled visit will be performed using a mixed effect model for repeated measures (MMRM) including fixed effects for treatment, visit, treatment by visit interaction, age group (12 to <18 years and ≥ 18 years), blood eosinophil counts at enrollment (300 to <400/ μL and $\geq 400/\mu\text{L}$), and sex, height and baseline value as covariates, and patient as a random effect. Age and blood eosinophil categories will be based on data recorded in the clinical database. An unstructured covariance matrix will be used for the within patient correlation modeling. If the fit of the unstructured (UN) covariance matrix fails to converge, the following covariance structures will be tried in order until convergence is reached: first order autoregressive (AR[1]) and compound symmetry (CS). Based on the MMRM model, the treatment effect, the difference from placebo, and the associated 95% CI will be presented together with the corresponding p-value.

The following sample SAS[®] code pertains to the MMRM analysis.

```
proc mixed data=<<>>;
  class patient visit treatment strata1 strata2 sex;
  model change=treatment strata1 strata2 sex height baseline visit treatment*visit
    /ddfm=kr alpha=0.05;
  repeated visit /type=un subject=patient r;
  lsmeans treatment*visit / diff cl;
  ods output lsmeans=<<>>;
  ods output diffs=<<>>;
run;
```

Model results will only be reported if there are at least 15 patients contributing to the analysis in each treatment group; otherwise only the descriptive statistics will be displayed. A line graph presenting the LS mean change from baseline over time (at each visit) will be provided for pre-bronchodilator FEV₁, [REDACTED] by treatment group.

Pre-bronchodilator FEV₁ at Week 52 will additionally be examined for the selected subgroups defined in Section 3.4. The analysis of subgroups will use a MMRM model similar to the one described above. Subgroups will be presented graphically using forest plots.

The proportion of patients achieving an increase of ≥ 100 mL in FEV₁ from baseline to each scheduled visit will be summarized. A stratified (based on randomization strata) Cochran-Mantel-Haenszel (CMH) test will be used to analyze the proportion of patients achieving an increase of ≥ 100 mL in FEV₁ from baseline to Week 52.

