6.3.9.1.5. Asthma control days

An asthma control day (y/n) is defined as a day on which the patient used ≤ 2 puffs of inhaled SABA therapy, had no nighttime awakenings, and experienced no CAEs or moderate exacerbations.

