6.3.9.2. Analysis

Compliance with the daily diary assessments will be derived for each patient as an additional measure of protocol adherence. A diary compliant day will be defined as a day with non-missing values for all diary assessments, including AM/PM asthma symptom score, [REDACTED],

[REDACTED]. Diary compliance will be derived as a percentage over the treatment period:

- $\text{Diary compliance (\%)} = 100 \times (\text{total number of diary compliant days} / \text{total number of days during the treatment period})$

The treatment period for diary compliance extends from the first day of study drug to the last day of study drug. Note that, in this analysis, missing data will be treated as non-compliant (eg, if compliance cannot be assessed for a given day due to missing data, then the day will not be counted as a diary compliant day).

[REDACTED]

A weekly average of the daily diary measures ([REDACTED], total asthma symptom score, and [REDACTED]) will be derived (see [Table 3](#) for the definition of analysis days for diary data). The average will be calculated as the sum of all values divided by the number of non-missing assessments. There will be no imputation of missing data. At least 4 of the 7 measurements need to be recorded for a week to be included in the analysis; otherwise the week will be treated as missing.

[REDACTED] and asthma control days will be derived and analyzed as percentages over the relevant analysis period, derived as:

- $\text{Asthma control days (\%)} = 100 \times (\text{total number of asthma control days} / \text{total number of days during the analysis period})$

[REDACTED]

The analysis periods are as defined in [Section 6.3](#). Note that, in this analysis, missing data will be treated as non-responders (eg, if asthma control cannot be assessed for a given day due to missing data, then the day will not be counted as an asthma control day).

Summary statistics of actual values and change from baseline to each week will be provided by treatment group.

Analysis of the change from baseline to each week will use a similar MMRM model as described in [Section 6.3.3.2](#) with the exception of inclusion of sex and height in the model.

Analysis of the percentage of [REDACTED] and percentage of asthma control days will be performed using an analysis of variance (ANOVA) model with fixed effects for treatment, age group, and blood eosinophil counts at enrollment.

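### Optional improvement: percentage of asthma control days could be adjusted for the run-in percentage; the planned ANOVA is valid, and the precision gain is probably small to moderate

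*SAP*

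**What the plan says.** The protocol (9.5.6.2) gives the model: "Analysis of percentage of asthma control days will use an analysis of variance (ANOVA) model with treatment group and stratification factors". SAP 6.3.9.2 repeats it: analysis of the "percentage of asthma control days will be performed using an analysis of variance (ANOVA) model with fixed effects for treatment", age group and eosinophil category. Part of the SAP sentence is redacted because it also covers another endpoint, but the list of model effects is complete and contains no baseline term.

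The other continuous secondary endpoints (FEV1, AQLQ +12, ACQ-6, total symptom score, SGRQ) use a repeated-measures model that includes the baseline value. For lung function the covariates are "sex, height and baseline value as covariates, and patient as a random effect"; the others drop sex and height but keep baseline. The protocol leaves room for more: "Additional covariates or factors may be added to the statistical models".

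An asthma control day (SAP 6.3.9.1.5) is one on which the patient used at most 2 puffs of SABA, "had no nighttime awakenings, and experienced no CAEs or moderate exacerbations". From visit 2, patients "complete daily self-monitoring of symptoms using an asthma control diary and PEF meter" (protocol 3.16.1). On the diary items, protocol 6.10 says "The number of times asthma rescue medication (number of inhalations/puffs) is used will be assessed by reviewing the asthma control diary", and 6.11 says "Patients will record nighttime awakenings due to asthma as indicated in the asthma control diary".

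**The concern.** Patients differ in how well controlled they are at entry, and some of that difference persists on treatment. Without a run-in term, the persistent part stays in the error variance and widens the confidence interval for the treatment difference. This is the only continuous secondary endpoint without such a term.

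The endpoint is fifth of nine secondaries in the fixed sequence (SAP 4.3 and 6.3.1). If it fails, four endpoints below it cannot be interpreted inferentially: SGRQ, time to first CAE, hospital or emergency exacerbations, and moderate exacerbations. The precision of this one test therefore matters beyond itself, but only if the primary and the first four secondaries have all succeeded.

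**Working it through.** **Can the covariate be derived?** Two of the three components, puffs and awakenings, are run-in diary items. The third is essentially absent, because inclusion criterion k bars randomisation after an exacerbation in screening or run-in that needed medication beyond extra SABA. SAP Table 3 already defines diary Days −7 to −1, and SAP 4.2.1 already uses a 4-of-7 rule for diary baselines. Criterion l requires 4 days of entries in the last 7, or an equivalent. That supports most patients but not all: the equivalent is undefined, and Table 3 pairs each evening with the next morning, so some entries will not form a full analysis day.

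**Figures in the plan.** The documents give no SD, effect size, power or correlation for this endpoint. Their only power statement concerns the primary endpoint. It reproduces at 99.8% with 225 per arm, rate 2.9, dispersion 1.2 and rate ratio 0.55, and has no bearing here.

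**Closed form.** With correlation r between run-in and on-treatment percentages:

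- variance factor = 1 − r²
- SE reduction = 1 − √(1 − r²)
- power, starting from an assumed 80% = Φ((1.960 + 0.842)/√(1 − r²) − 1.960)
- equivalent patients per arm = 225/(1 − r²)

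| assumed r | variance factor | SE reduction | power (from 80%) | equivalent n per arm |
|---|---|---|---|---|
| 0.1 | 0.99 | 0.5% | 80.4% | 227 |
| 0.2 | 0.96 | 2.0% | 81.6% | 234 |
| 0.3 | 0.91 | 4.6% | 83.6% | 247 |
| 0.5 | 0.75 | 13.4% | 89.9% | 300 |

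The cost is one degree of freedom. With 450 patients and four fitted parameters there are 450 − 4 = 446. Break-even is 1 − r² = 445/446, so r = 0.047.

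**What r might be.** Seven days is a coarse window, and criterion l selects on poor control in those same days. A simulation examined this with every input assumed: N = 450, no treatment effect, logit-normal control propensity with SD 1.5, 364 treatment days with missing days counted as not controlled, 7 run-in days with at least 4 recorded and 15% missing on average, and 400 runs per cell. SE reductions were:

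| selection at entry | latent correlation 0.3 | 0.5 | 0.7 |
|---|---|---|---|
| none | 2.8% | 8.3% | 18.0% |
| half of candidates qualify by another route; the rest need ≥3 uncontrolled recorded days | 2.4% | 7.6% | 16.4% |
| all patients need ≥3 uncontrolled recorded days | 0.9% | 3.1% | 7.4% |

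The last row is extreme. The four conditions in criterion l are alternatives, and daytime symptoms, one or two puffs of SABA, or FEV1 below 80% predicted can each satisfy it without any uncontrolled day.

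A second simulation with different assumed inputs (2,000 trials per setting, 5% of run-in values missing and filled with the overall mean) gave variance ratios of 0.95, 0.84 and 0.70 at observed r of about 0.24, 0.41 and 0.57. The closed form gives 0.94, 0.83 and 0.68.

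**Validity.** In the second simulation, type I error was 4.6% to 5.6% for the ANOVA and 4.6% to 5.5% for the ANCOVA with mean fill (Monte Carlo SE about 0.5 points).

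**Missing covariate values.** Dropping the 5% of patients without a run-in value can undo the gain. At r of about 0.24, power was 78.4% for ANOVA, 80.0% for ANCOVA with mean fill and 77.4% for complete-case ANCOVA.

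**Missing run-in days.** Rule A takes the percentage of recorded days, with at least 4 of 7 recorded. Rule B counts a missing day as not controlled, as the endpoint does. In the first simulation, without selection, A was better by 0.2 to 1.1 points of SE reduction when compliance was equal across patients. B was better by 1.1 to 2.6 points when each patient's compliance persisted from run-in into treatment.

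**The case against.** The strongest reply is that ANOVA was a recorded choice. The Amendment 02 log, at 24 patients enrolled, shows the endpoint moving from a change in percentage to the plain percentage and the model moving from ANCOVA to ANOVA. The SAP also considered covariates endpoint by endpoint, adding sex and height for lung function only. This stands as evidence that the omission was not an oversight. It is not an argument against the covariate: the reason given is alignment with the SAP, and a plain percentage can be adjusted for a pre-randomisation measure as readily as a change score.

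Second, the gain cannot be known from the documents. That is correct. Calling it small to moderate is a judgement that fits r of roughly 0.2 to 0.5. At r = 0.1 it is negligible; at 0.6 the variance would fall by 36%.

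Third, a 7-day window limits r although at least three weeks of run-in diary are collected. That is fair. A longer prespecified window is a reasonable alternative; seven days is proposed because the SAP already defines it.

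Fourth, the change is not wholly without cost: it needs a new derived variable, a missing-day rule and a fill. True, but these are minor.

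**Conclusion.** The point holds as an optional, low-priority improvement. The planned test is valid, the protocol and SAP agree, and nothing has to be corrected. A run-in covariate would reduce the standard error by 0.5% to 13.4% for r between 0.1 and 0.5, more likely in the lower part of that range, at the price of one degree of freedom. The size rests on an assumed r, and the power figures on an assumed 80% starting point. Confidence in the size is medium; confidence that adjustment costs almost nothing in precision is higher, since break-even is at r = 0.047.

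**What to change.** Before unblinding, amend SAP 6.3.9.2 so that percentage of asthma control days is analysed by ANCOVA with treatment, age group, eosinophil category and the run-in percentage of asthma control days over diary Days −7 to −1 of Table 3. If the redacted endpoint in the same sentence is to stay on ANOVA, separate the two.

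Prespecify either rule A or rule B for missing run-in days. Both are valid because the covariate is measured before randomisation. For any patient without a derivable value, substitute the overall mean across both arms so that every patient in the analysis set is kept. State this as an exception to SAP 4.2.1, which treats such a baseline as missing, and to SAP 4.4, which plans no estimation of missing data for this endpoint.

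The endpoint is unchanged, no new data are needed, and protocol 9.5.6.2 already permits added covariates. The cost is one derived variable, one model term and the two stated exceptions. If the codes have already been opened, report the adjusted model as supportive only.

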7. SAFETY ANALYSIS

7.1. General

The safety analysis set will be used for all safety analyses, unless otherwise noted. Summaries will be presented by treatment group actually received.

In this study, patients are encouraged to remain in the study and complete the remaining study assessments even after withdrawing from treatment. The assessment of safety in this context will be based on measurements and events recorded during the treatment period (on-treatment). On-treatment assessments will be defined as events and measurements occurring between the first dose of study drug and the end of treatment (week 52) visit for patients who complete treatment and between the first dose of study drug and the last dose of study drug + 4 weeks for patients who discontinued treatment early.

7.2. Study Drug Administration

The exposure to study drug will be characterized by duration of treatment and by the number of patients receiving at least 1, 2, 3, etc. injections. Total patient years will also be summarized. The summaries will be provided by treatment group and overall, and by baseline stratification factors.

Duration of treatment period is defined separately for patients who completed/discontinued treatment.

- Completed: End of treatment (week 52) visit date – first dose date + 1
- Discontinued: Last dose date – first dose date + 29

7.3. Adverse Events

Adverse events will be coded using the Medical Dictionary for Regulatory Activities (MedDRA); the final version number will be indicated in the summary tables.

On-treatment adverse event summaries will be presented by treatment group and overall, based on events with onset during the treatment period. If the AE start date is missing or partial, the event will be considered on-treatment unless there is evidence to the contrary (eg, month and year of AE start is present and is less than the month and year of the first dose of study drug). Post-treatment adverse events with onset during the follow-up period (ie, AE start date greater than the upper bound of the treatment period, as described previously) will be summarized separately.

Summaries will be presented by SOC and/or PT for all adverse events (overall and by severity), adverse events determined by the investigator to be related to study treatment (overall and by severity), serious adverse events, adverse events causing discontinuation from study treatment, and non-serious adverse events. Treatment related adverse event summaries will include events with missing relationship to study drug. For summaries by severity, patients will be counted at the greatest reported severity. Adverse events missing the flag indicating a serious adverse event will be excluded from the summary of serious adverse events, but included in the summary of non-serious adverse events.

In addition, adverse events that begin within 24 hours after study drug injection and injection-site adverse events (as recorded on the CRF) will each be summarized separately.

Summaries for the most common adverse events (incidence $\geq 2\%$ in reslizumab-treated patients) and adverse events occurring with greater frequency for reslizumab-treated patients compared to placebo will also be presented.

All adverse events, including pre-treatment events, will be included in the patient listings. The mapping of MedDRA dictionary terms for adverse event descriptions will also be provided.

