**Statistical Considerations:**

**Sample Size Rationale:**

Power calculations were based on the below assumptions:

- Negative binomial (NB) distribution for the number of exacerbations with a mean of 2.9 exacerbations per patient per year for the placebo group
- Dispersion parameter of 1.2
- Treatment effect of 45% between the reslizumab group and the placebo group
- Alpha level of 0.05

Based on the assumptions above, 225 patients per arm (450 total) will provide >99% power to detect significant treatment effect of reslizumab over placebo in the reduction of exacerbation rate. The sample size was increased beyond the minimal sample size required to provide 90% power in order to allow sufficient number of patients to assess safety and immunogenicity and to ensure adequate enrollment in the adolescent subset. The current sample size also provide higher power for other efficacy endpoints.

**Analysis of Primary Endpoint:** The primary analysis of frequency of CAEs will use the NB regression model. The primary NB model will include the treatment group, randomization stratification factors, and number of exacerbations in the previous year as model factors and an offset variable. The offset variable will be calculated as the logarithm of follow-up duration minus the summed duration of exacerbations. The ratio of CAE rate between the treatment groups and its 95% confidence interval (CI) will be estimated from the NB model.

Data from all randomized patients will be used in the primary analyses regardless of whether they early withdrew from treatment or completed the treatment phase.

**Analysis of Secondary Endpoints:** Analysis of pulmonary function tests, AQLQ +12, ACQ-6, total asthma symptom scores, and SGRQ will use the mixed model repeated measures model with treatment group, visit,

treatment and visit interaction, baseline value, and stratification factors as fixed effects and patient as a random effect. Analysis of percentage of asthma control days will use an analysis of variance (ANOVA) model with treatment group and stratification factors.

Additional covariates or factors may be added to the statistical model. These will be detailed in the statistical analysis plan.

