### **3. STUDY DESIGN**

#### **3.1. General Design and Study Schema**

This is a 52-week, Phase 3, multicenter, randomized, double-blind, placebo-controlled study to evaluate the safety and efficacy of reslizumab, at a fixed dose of 110 mg, administered sc every 4 weeks in patients aged 12 years and older with asthma and elevated blood eosinophils, who are inadequately controlled on at least a medium total daily ICS dose and a second asthma controller.

Evidence of inadequate asthma control will include a history of at least 2 exacerbations requiring systemic corticosteroids (oral or injection) in the previous 12 months, a suboptimal screening ACQ-6 score ( $\geq 1.5$ ), and persistent symptoms during run-in on the patient's usual asthma controller regimen. At least one of the historical exacerbations must have been previously documented in the medical or pharmacy record; additional exacerbations may have been documented in either the medical or pharmacy record, or may be documented by the study site at the time of screening history. For all exacerbations, which fulfill inclusion criterion 'c', the approximate dates of systemic corticosteroid therapy and the name of the systemic corticosteroid taken should be recorded in source documents. The study consists of a screening period of up to 2 weeks to satisfy essential screening inclusion criteria (ie, confirmation of asthma with elevated blood eosinophils), a minimum 3-week run-in period on usual care to establish the patient's baseline level of control and a 52-week double-blind treatment period. If the patient enrolls in an available open-label, long-term safety study, then adults (age 18 years and older) may wait to complete the early and late follow-up visits until the end of the open-label study; however, adolescents (ages 12 to <18 years) should complete the early follow-up visit at 12 weeks as part of this current study before starting an open-label study.

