### **7.1.2. Recording and Reporting Adverse Events**

For adverse event recording, the study period is defined for each patient as that time period from signature of the informed consent form through the end of the follow-up period. For this study, the follow-up period is defined as 12 weeks after the EOT visit. Adverse events will be collected at each visit, including the follow-up visit, via adverse event inquiry.

All adverse events that occur during the defined study period must be recorded on the source documentation and transcribed onto the CRF, regardless of the severity or seriousness of the event or judged relationship to the study drug. For serious adverse events, the Serious Adverse Event Form must also be completed and the serious adverse event must be reported immediately (see Section 7.1.5.3.1). The investigator does not need to actively monitor patients for adverse events once the study has ended. Serious adverse events that occur to a patient after the end of study should be reported to the sponsor if the investigator becomes aware of them, following the procedures described in Section 7.1.5.3.1.

At each contact with the patient, the investigator or designee must question the patient about adverse events by asking an open-ended question such as, “Have you had any unusual symptoms or medical problems since the last visit? If yes, please describe.” In addition, the eDiary will be programmed to query the patient about symptoms potentially consistent with hypersensitivity occurring during the 24 hour period following study drug injection. All reported or observed signs and symptoms will be recorded individually, except when considered manifestations of a medical condition or disease state. A precise diagnosis will be recorded whenever possible. When such a diagnosis is made, all related signs, symptoms, and any test findings will be recorded collectively as a single diagnosis on the CRF and, if it is a serious adverse event, also on the Serious Adverse Event Form.

The clinical course of each adverse event will be monitored at suitable intervals until resolved, stabilized, returned to baseline, or until the patient is referred for continued care to another health care professional, or until a determination of a cause unrelated to the study drug or study procedure is made.

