### **9.10. Immunogenicity Analysis**

Anti-reslizumab antibody information will be described for subjects who test positive. Samples from placebo-treated patients will not be analyzed unless the patient elects to enroll into an available open-label safety study where the patient will receive reslizumab treatment. In this case the pre-dose (baseline) sample from the rolled-over placebo patient will be analyzed and reported along with post-treatment samples collected in the open-label safety study. Summaries will be provided if appropriate.

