8.2. Pharmacodynamic Analysis

8.2.1. Target Biomarker (Blood Eosinophil Counts)

The target biomarker endpoints are the blood eosinophil counts at baseline/DoR; weeks 2, 4, 8, 12, 16, 32, 52 or early withdrawal; and the follow-up visit (approximately week 64).

Summary statistics of actual values, change from baseline, and percent change from baseline to each scheduled visit will be provided by treatment group, using the ITT analysis set. A line graph will be provided summarizing the mean blood eosinophil counts at each visit.

Blood eosinophils will additionally be examined for selected subgroups defined in Section 3.4. As described above, the analysis of eosinophils by subgroups will be summarized descriptively.

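### The post-treatment adverse-event table does not stop at the first open-label reslizumab dose and has no follow-up-based denominator, so adults who roll over either dilute it or contribute events on active drug to their original arm

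*SAP*

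**What the plan says.** **The table.** SAP 7.3 gives a separate summary of "Post-treatment adverse events with onset during the follow-up period (ie, AE start date greater than the upper bound of the treatment period". The only operational test is the start date. For completers the bound comes from SAP 7.1, which takes on-treatment events as those "between the first dose of study drug and the end of treatment (week 52) visit for patients who complete treatment". For patients who stop early it is the last dose plus 4 weeks.

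**The population.** SAP 7.1 states: "The safety analysis set will be used for all safety analyses, unless otherwise noted". Under SAP 3.2 that set is every patient who received a dose. Nothing in the SAP removes or censors patients who move to the open-label study.

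**Rollover.** Protocol 3.1 says that, on entering the open-label study, "adults (age 18 years and older) may wait to complete the early and late follow-up visits until the end of the open-label study". Adolescents should have the 12-week visit in this study first. Protocol 3.16.4 lets these adults make the follow-up visits within the other study and be regarded as complete at week 52. SAP 5.2 also counts extension participants as complete at week 52. Protocol 9.10 shows that open-label treatment is active drug for former placebo patients too, since it covers the case where "the patient elects to enroll into an available open-label safety study where the patient will receive reslizumab treatment".

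**Recording window.** Protocol 7.1.2 runs each patient's adverse-event period to the end of follow-up: "For this study, the follow-up period is defined as 12 weeks after the EOT visit". It makes no exception for rollover.

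**Eosinophils.** SAP 8.2.1 lists "and the follow-up visit (approximately week 64" among the target biomarker time points.

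**The concern.** Protocol 9.7.2 describes these events as arising after study treatment has ended, so a reader will take the table as off-drug experience. An adult who goes straight on to open-label reslizumab has no such experience, or only the gap before the first open-label dose. The SAP takes account of the extension when it defines study completion, but carries nothing across to the adverse-event rule.

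The off-drug period is where late reactions or effects of stopping would appear. Week 64 is 16 weeks after the last dose, and Protocol 1.3.2.2 reports that in completed studies mean eosinophil counts were back at baseline about 4 months after the last dose. A table that counts unobserved patients, or mixes in active-drug time, can obscure what happens then.

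**Working it through.** **1. The plan's own timings.** Screening 2 + run-in 3 + treatment 52 + follow-up 12 = 69 weeks, which matches the stated participation of about 69 weeks. The follow-up visit is at 52 + 12 = week 64. The last dose is at week 48, so week 64 is 64 − 48 = 16 weeks after it. The 69 weeks therefore include a 12-week follow-up that a rollover adult need not spend off drug.

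**2. The provisions side by side.**
- Protocol 3.16.4 and SAP 5.2: a rollover adult may be finished with this study at week 52.
- Protocol 7.1.2: every patient's adverse events are recorded to 12 weeks after the end-of-treatment visit.
- SAP 7.3: any recorded event starting after the treatment period is post-treatment, on the whole safety set.

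The documents do not say which of the first two governs, or whether events on open-label drug enter this study's database. They also do not give the timing of the first open-label dose.

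**3. Reading A: open-label events are recorded only in the other study.** Let r be the share of an arm that rolls over at week 52 with no off-drug time, and p the incidence among patients who are followed. Crude incidence = p(1 − r). Both inputs are assumptions. With p = 10%:
- r = 20%: 0.10 × 0.80 = 8%
- r = 50%: 0.10 × 0.50 = 5%
- r = 80%: 0.10 × 0.20 = 2%

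If r is the same in both arms, both incidences shrink by the same factor and their ratio is kept. If r differs, the ratio moves: a true 10% in both arms with r = 20% in one and 50% in the other reads 8% against 5%.

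**4. Reading B: open-label events are recorded in this study.** Let q be the incidence on open-label drug over the same window. The share of an arm's post-treatment events that occurred on open-label reslizumab is rq / [rq + (1 − r)p].
- p = q = 10%: the share equals r, so 20%, 50% and 80%.
- p = 10%, q = 20%: 0.04/0.12 = 33%, 0.10/0.15 = 67% and 0.16/0.18 = 89%.

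In the placebo column these would be events on active drug.

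**5. Early discontinuers.** Protocol 4.4.1 asks them to stay to week 52 and to attend a visit 12 weeks later. A patient who stops after one dose leaves the treatment period at week 4 and can be followed to week 64, which is 60 weeks of post-treatment time. A non-rollover completer has 12. A crude percentage treats the two alike, whatever happens with rollover.

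**6. Does person-time repair it?** Take 225 patients in an arm, p = 10% and 12 weeks off drug for each non-rollover patient, counting one event per affected patient.

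| r | followed | with event | off-drug years (followed × 12/52) | rate per patient-year |
|---|---|---|---|---|
| 20% | 180 | 18 | 41.5 | 0.43 |
| 50% | 112.5 | 11.25 | 26.0 | 0.43 |
| 80% | 45 | 4.5 | 10.4 | 0.43 |

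The rate no longer depends on r. What changes is how much follow-up supports it.

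**The case against.** The strongest reply is that the plan can be read harmlessly. Adults who roll over may be complete at week 52 and make later visits in the other study, so their later events plausibly belong there. SAP 7.3 also confines the table to the follow-up period, which Protocol 7.1.2 limits to 12 weeks. A reader might infer that the plan definitely places reslizumab events in the placebo column. The documents do not support that, because no provision says open-label events reach this database. The reply does not rescue the table, however. If those events stay elsewhere, the denominator problem of Reading A remains, and open-label dosing can fall inside the 12 weeks.

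A reader might also infer that the week-64 eosinophil summary includes rollover patients. It need not. SAP 4.4 uses observed data only, so an adult who defers the visit is missing at week 64. SAP 3.1 and 4.5 make the on-treatment approach the main one for by-visit efficacy summaries, and SAP 3.4.1 lists eosinophils among efficacy endpoints, so it is unclear whether week 64 is summarised at all. What remains is a selected sample at that visit and no rule for a deferred one.

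Three further points stand. The rollover shares are assumed. Equal rollover leaves the ratio between arms intact, and no difference in rollover between arms is shown. Safety is assessed on-treatment by default, and all events are also listed by patient.

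**Conclusion.** The concern holds within limits. Under either reading, the post-treatment adverse-event table does not measure off-drug experience for adults who roll over. Under Reading A the crude incidence is multiplied by 1 minus the rollover share; under Reading B an unknown part of each column is active-drug experience. Which reading applies depends on two provisions that the documents leave unreconciled. The illustrative sizes rest on assumed rollover shares of 20%, 50% and 80%, assumed incidences of 10% and 20%, and open-label dosing that starts at about week 52.

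The reach is narrow. Adolescents who complete the 12-week visit first, as they should, are unaffected. One descriptive safety table is involved. The primary analysis, the testing hierarchy and the on-treatment safety results do not change. It is still worth correcting, because the better method is specific and cheap. A bias in the comparison between arms is possible if rollover differs by arm, but it is not demonstrated.

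**What to change.** - **Reconcile** Protocol 3.16.4 and SAP 5.2 with Protocol 7.1.2: state whether adverse-event recording in this study ends at week 52 or at the first open-label dose for adults who roll over, and where later events are held.
- **SAP 7.3:** end post-treatment follow-up at the first open-label dose. Report by arm the number of patients with off-drug follow-up and the number who rolled over. Give events per patient-year of off-drug follow-up, which also deals with the longer post-treatment time of early discontinuers.
- **SAP 8.2.1:** state that samples taken after open-label dosing are not assigned to week 64, and whether week 64 is summarised.

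Excluding all rollover patients is not needed. Truncation keeps whatever valid off-drug time they contribute and avoids selecting on a choice made after randomisation.

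The cost is a few sentences in the SAP and one extra date, that of the first open-label dose. The table will rest on less follow-up time.
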